9.2 Target Lesions

All measurable lesions up to a maximum of 2 lesions per organ and 5 lesions in total, representative of all involved organs, will be identified as target lesions and recorded and measured at baseline. Target lesions will be selected on the basis of their size. Lesions with the longest diameter (short axis for lymph nodes) and are ≥ 10 mm (CT and MRI), ≥ 15 mm lymph nodes, > 20 mm CXR and are for accurate repetitive measurements (either by imaging techniques or clinically) will be chosen. A sum of the longest diameter (short axis for lymph nodes) of all target lesions will be calculated and reported as the baseline sum diameters. This will be used as reference to further characterize the objective tumor response of the measurable dimension of the disease.

- **Complete Response (CR):** Disappearance of all target lesions. Any lymph nodes must have a reduction in short axis to < 10 mm. Changes in tumor measurements must be confirmed by repeat studies performed no less than 6 weeks after the criteria for response are first met.

- **Partial Response (PR):** At least a 30% decrease in the sum of diameters of target lesions, taking as reference the baseline sum diameters. Changes in tumor measurements must be confirmed by repeat studies performed no less than 6 weeks after the criteria for response are first met.
- **Progressive Disease (PD):** At least a 20% increase in the sum of diameters of target lesions, taking as references the smallest sum on study (this includes the baseline sum if that is the smallest on study). In addition to the relative increase of 20%, the sum must also demonstrate an absolute increase of at least 5 mm. The appearance of one or more new lesions is also considered progression.
- **Stable Disease (SD):** Neither a sufficient shrinkage to qualify for PR nor sufficient increase to qualify for PD, taking as reference the smallest sum diameter while on study. Participants having a documented response with no confirmation of the response will be listed with stable disease.

9.3 Non-Target Lesions

All other small lesions (longest diameter < 10 mm or lymph nodes \geq 10 mm to < 15 mm short axis) and non-measurable lesions (i.e., leptomeningeal disease, ascites, pleural or pericardial effusion, inflammatory breast disease, lymphangitic involvement of skin or lung, blastic bone lesions, or abdominal masses / abdominal organomegaly identified by physical exam that is not measurable by imaging) should be identified as non-target lesions and indicated as present in the source documents at baseline. The general location will also be documented on the images drawing a regularly-shaped Region of Interest. Measurements of the non-target lesions will not be performed, but the presence or absence of each should be noted throughout follow-up and evaluation.

- **Complete Response:** Disappearance of all non-target lesions and normalization of tumor marker level, if applicable. All lymph nodes must be non-pathological in size (< 10 mm short axis).
- **Non-Complete Response/Non-Progressive Disease:** Persistence of 1 or more non-target lesion(s) and/or maintenance of tumor marker level above the upper limits of normal.
- **Progressive Disease:** Appearance of 1 or more new lesions or the unequivocal progression of existing non-target lesions. Although a clear progression of non-target lesions is exceptional, in such circumstances, the opinion of the treating physician should prevail and the progression status should be confirmed at a later time.

9.4 Evaluation of Response

Time point response assessments will be performed every 9 weeks. To determine time point response, refer to **Table 6** and **Table 7** below.

Table 6 Time Point Response Criteria: target (+/- non-target disease)

Target Lesions	Non-Target Lesions	New Lesions	Overall Response
CR	CR	No	CR
CR	Non-CR/Non-PD	No	PR
CR	Not evaluated	No	PR
PR	Non-PD or not all evaluated	No	PR
SD	Non-PD or not all evaluated	No	SD
Not all evaluated	Non-PD	No	NE
PD	Any	Yes or No	PD
Any	PD	Yes or No	PD
Any	Any	Yes	PD

Table 7 Time Point Response Criteria: non-target disease only

Non-Target Lesions	New Lesions	Overall Response
CR	No	CR
Non-CR/non-PD	No	Non-CR/non-PD ¹
Not all evaluated	No	NE
Unequivocal PD	Yes or No	PD
Any	Yes	PD

¹ Non-CR/non-PD is preferred over SD for non-target disease since SD is used as endpoint for assessment of efficacy in trials so to assign this category when no lesions can be measured is not advised.

The best overall response is the best response recorded from the start of study treatment until disease progression/recurrence or study discontinuation, taking into account any requirement for confirmation. In general, the participant's best response assignment will depend on the achievement of both measurement and confirmation criteria and will be determined by combining the participant's status of target lesions, non-target lesions, and new lesions.

- Symptomatic Deterioration: Participants with global deterioration of health status requiring discontinuation of treatment without objective evidence of disease progression at that time, and not related to study treatment or other medical conditions should be reported as progressive disease due to "symptomatic deterioration." Every effort should be made to document objective progression even after discontinuation of treatment due to symptomatic deterioration. Symptomatic deterioration that may lead to discontinuation of treatment include, but is not limited to, symptoms such as:
 - Weight loss > 10% of body weight.
 - Worsening of disease-related symptoms (e.g., worsening dyspnea, increasing pain/increasing requirement for narcotic analgesics).
 - Decline in performance status of > 1 level on ECOG scale.

9.5 Confirmation Measurement

A confirmatory assessment is required no less than 6 weeks after a PR or CR is deemed.

9.6 Guidelines for Evaluation of Measurable Disease

All measurements should be taken and recorded in metric notation using a ruler or calipers. All baseline evaluations should be performed as closely as possible to the beginning of treatment and never more than 4 weeks before the beginning of the treatment.

The same method of assessment and the same technique should be used to characterize each identified and reported lesion at baseline and during follow-up. Imaging-based evaluation is preferred to evaluation by clinical examination unless the lesion(s) being followed cannot be imaged but are assessable by clinical exam.

- **Clinical Lesions:** Clinical lesions will only be considered measurable when they are superficial (e.g., skin nodules and palpable lymph nodes) and ≥ 10 mm diameter as assessed using calipers (e.g., skin nodules). In the case of skin lesions, documentation by color photography, including a ruler to estimate the size of the lesion, is recommended.
- **Chest x-ray:** Lesions on chest x-ray are acceptable as measurable lesions when they are clearly defined and surrounded by aerated lung. However, CT is preferable.
- **Conventional CT and MRI:** This guideline has defined measurability of lesions on CT scan based on the assumption that CT slice thickness is 5 mm or less. If CT scans have slice thickness greater than 5 mm, the minimum size for a measurable lesion should be twice the slice thickness. MRI is also acceptable in certain situations (e.g., for body scans).

Use of MRI remains a complex issue. MRI has excellent contrast, spatial, and temporal resolution; however, there are many image acquisition variables involved in MRI, which greatly impact image quality, lesion conspicuity, and measurement. Furthermore, the availability of MRI is variable globally. As with CT, if an MRI is performed, the technical specifications of the scanning sequences used should be optimized for the evaluation of the type and site of disease. Furthermore, as with CT, the modality used at follow-up should be the same as was used at baseline and the lesions should be measured/assessed on the same pulse sequence. It is beyond the scope of the RECIST guidelines to prescribe specific MRI pulse sequence parameters for all scanners, body parts, and diseases. Ideally, the same type of scanner should be used and the image acquisition protocol should be followed as closely as possible to prior scans. Body scans should be performed with breath-hold scanning techniques, if possible.

- **PET-CT:** At present, the low dose or attenuation correction CT portion of a combined PET-CT is not always of optimal diagnostic CT quality for use with RECIST measurements. However, if the site can document that the CT performed as part of a PET-CT is of identical diagnostic quality to a diagnostic CT (with IV and oral contrast), then the CT portion of the PET-CT can be used for RECIST measurements and can be used interchangeably with conventional CT in accurately measuring cancer lesions over time. Note, however, that the PET portion of the CT introduces additional data which may bias an investigator if it is not routinely or serially performed.

- **Ultrasound:** Ultrasound is not useful in assessment of lesion size and should not be used as a method of measurement. Ultrasound examinations cannot be reproduced in their entirety for independent review at a later date and, because they are operator dependent, it cannot be guaranteed that the same technique and measurements will be taken from one assessment to the next. If new lesions are identified by ultrasound in the course of the study, confirmation by CT or MRI is advised. If there is concern about radiation exposure at CT, MRI may be used instead of CT in selected instances.
- **Endoscopy, Laparoscopy:** The utilization of these techniques for objective tumor evaluation is not advised. However, such techniques may be useful to confirm complete pathological response when biopsies are obtained or to determine relapse in trials where recurrence following complete response (CR) or surgical resection is an endpoint.
- **Tumor Markers:** Tumor markers alone cannot be used to assess response. If markers are initially above the upper normal limit, they must normalize for a participant to be considered in complete clinical response.
- **Cytology, Histology:** These techniques can be used to differentiate between partial responses (PR) and complete responses (CR) in rare cases (e.g., residual lesions in tumor types, such as germ cell tumors, where known residual benign tumors can remain).

The cytological confirmation of the neoplastic origin of any effusion that appears or worsens during treatment when the measurable tumor has met criteria for response or stable disease is mandatory to differentiate between response or stable disease (an effusion may be a side effect of the treatment) and progressive disease.

- **FDG-PET:** While FDG-PET response assessments need additional study, it is sometimes reasonable to incorporate the use of FDG-PET scanning to complement CT scanning in assessment of progression (particularly possible 'new' disease). New lesions on the basis of FDG PET imaging can be identified according to the following algorithm:
- Negative FDG-PET at baseline, with a positive FDG-PET at follow-up is a sign of PD based on a new lesion.
- No FDG-PET at baseline and a positive FDG-PET at follow-up: If the positive FDG-PET at follow-up corresponds to a new site of disease confirmed by CT, this is PD. If the positive FDG-PET at follow-up is not confirmed as a new site of disease on CT, additional follow-up CT scans are needed to determine if there is truly progression occurring at that site (if so, the date of PD will be the date of the initial abnormal FDG-PET scan). If the positive FDG-PET at follow-up corresponds to a pre-existing site of disease on CT that is not progressing on the basis of the anatomic images, this is not PD.
- FDG-PET may be used to upgrade a response to a CR in a manner similar to a biopsy in cases where a residual radiographic abnormality is thought to represent fibrosis or scarring. The use of FDG-PET in this circumstance should be prospectively described in the protocol and supported by disease-specific medical literature for the indication. However, it must be acknowledged that both approaches may lead to false positive CR due to limitations of FDG-PET and biopsy resolution/sensitivity.

Note: A ‘positive’ FDG-PET scan lesion means one which is FDG avid with an uptake greater than twice that of the surrounding tissue on the attenuation corrected image.

10 SAFETY EVALUATION

10.1 Adverse Events

10.1.1 Definition

An adverse event or adverse experience (AE) is any untoward medical occurrence associated with the use of a drug in humans, whether or not considered drug related. Therefore, an AE can be ANY unfavorable and unintended sign (including an abnormal laboratory finding), symptom, or disease temporally associated with the use of a medicinal (investigational) product, whether or not considered related to the medicinal (investigational) product (attribution of ‘unrelated’, ‘unlikely’, ‘possible’, ‘probable’, or ‘definite’).

An AE is considered “unexpected” if it is not listed in the investigator brochure or is not listed at the specificity or severity that has been observed; or if an investigator brochure is not required or available, is not consistent with the risk information described in the general investigational plan in other study-related documents.

10.1.1.1 Diagnosis Versus Signs and Symptoms

If known, a diagnosis should be recorded on the CRF rather than individual signs and symptoms (e.g., record only liver failure or hepatitis rather than jaundice, asterix, and elevated transaminases). However, if a constellation of signs and/or symptoms cannot be clinically characterized as a single diagnosis or syndrome at the time of reporting, each individual event should be recorded as an AE or SAE on the CRF. If a diagnosis is subsequently established, it should be reported as follow-up information.

10.1.1.2 Adverse Events Occurring Secondary to Other Events

In general, AEs occurring secondary to other events (e.g., cascade events or clinical sequelae) should be identified by their primary cause. For example, if severe diarrhea is known to have resulted in dehydration, it is sufficient to record only diarrhea as an AE or SAE on the CRF.

However, clinically significant AEs occurring secondary to an initiating event that are separated in time should be recorded as independent events on the CRF. For example, if a severe gastrointestinal hemorrhage leads to renal failure, both events should be recorded separately on the CRF.

10.1.1.3 Abnormal Laboratory Values

Only clinically significant laboratory abnormalities that require active management will be recorded as AEs or SAEs on the CRF (e.g., abnormalities that require study drug dose modification, discontinuation of study treatment, more frequent follow-up assessments, further diagnostic investigation, etc.).

If the clinically significant laboratory abnormality is a sign of a disease or syndrome (e.g., alkaline phosphatase and bilirubin 5 x the upper limit of normal associated with cholecystitis), only the diagnosis (e.g., cholecystitis) needs to be recorded on the Adverse Event CRF.

If the clinically significant laboratory abnormality is not a sign of a disease or syndrome, the abnormality itself should be recorded as an AE or SAE on the CRF. If the laboratory abnormality can be characterized by a precise clinical term, the clinical term should be recorded as the AE or SAE. For example, an elevated serum potassium level of 7 mEq/L should be recorded as “hyperkalemia.”

Observations of the same clinically significant laboratory abnormality from visit to visit should not be repeatedly recorded as AEs or SAEs on the CRF, unless their severity, seriousness, or etiology changes.

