3 OBJECTIVES

3.1 Primary Objectives

- To estimate the objective response rate of patients with metastatic colorectal cancer treated with pembrolizumab and cetuximab.
- To estimate the 6-month PFS rate of patients with metastatic colorectal cancer treated with pembrolizumab and cetuximab.
- To examine the adverse event profile of combining pembrolizumab and cetuximab.

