4.1.1 Phase Ib\II

There will be an initial phase Ib cohort to examine the safety and tolerability of the combination. Study progress will be monitored regularly by the RPCI Phase I Committee. After up to 9 patients are enrolled, and a minimum of 6 have completed at least two cycles of chemotherapy, the study will be suspended, and the safety/tolerability of the combination will be examined. At that time, the study team will decide what action to take, e.g., continue the study as is, make changes to the study with regard to treatment or dose modifications, or discontinue the study. Once analysis is complete and a safe treatment plan has been established, the phase II study will commence.

The Phase II study will enroll patients with metastatic colorectal cancer who are eligible for anti-EGFR therapy (i.e. RAS wt, no known expanded KRAS or NRAS mutations, anti-EGFR therapy naïve or appropriate for anti-EGFR rechallenge). For the purposes of the study, a cycle will be defined as three weeks. Patients will be treated with cetuximab, administered weekly and pembrolizumab, administered every 3 weeks as described in **Section 6**. A regimen of pre-emptive skin care is recommended, as described in **Section 6.4**. Disease assessments will occur every 9 weeks to assess response, using RECIST v 1.1. As described in **Section 6.1**, after initial progressive disease, if fulfilling certain criteria, patients may continue on therapy with further response assessments in line with irRECIST criteria (**Appendix D**). Per local policy, a consent addendum should be obtained to continue on treatment past progression. Progression free survival and objective response rate will be observed. Additional blood based biomarker tests will be performed prior to treatment, at 4 weeks (cycle 2, day 1) and 10 weeks (cycle 4, day 1). A mandatory biopsy will be performed prior to treatment; a secondary biopsy at approximately 10 weeks (cycle 4, day 1) will be optional, but strongly encouraged. However, in order to obtain sufficient samples for informative analysis, for the final 10 patients of the study, both biopsies will be mandatory.

Primary Endpoints

- Six-month progression free survival and objective tumor response rate will be evaluated according to RECIST 1.1 guidelines after every 3 cycles (9 weeks) of treatment.

- Adverse events will be categorized and graded according to NCI CTCAE v4.0.

Secondary Endpoints

- Progression-free survival
- Overall survival

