6.4.2 Hypomagnesemia

Anti-EGFR therapies such as cetuximab have an established link to hypomagnesemia. Magnesium levels are to be monitored and levels replaced on therapy and up to 8 weeks after completion of therapy, as per practice standard.

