12.4 Safety Analysis

12.4.1 Adverse Event

The frequency of toxicities will be tabulated by maximum grade by preferred term within a patient across all cycles. All participants who receive any study treatment will be considered evaluable for toxicity.

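### Laboratory toxicities reach the safety table only through an investigator-judgement filter, and the scheduled values that could check that filter are not analysed

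*Combined protocol and SAP*

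**What the plan says.** - **Objective (3.1).** The third primary objective reads: "To examine the adverse event profile of combining pembrolizumab and cetuximab". It carries no test or threshold. Section 4.1.1 adds: "Adverse events will be categorized and graded according to NCI CTCAE v4.0".
- **Definition (10.1.1).** An adverse event can be "ANY unfavorable and unintended sign (including an abnormal laboratory finding), symptom, or disease temporally associated" with use of the product, whether or not it is considered related.
- **CRF rule (10.1.1.3).** "Only clinically significant laboratory abnormalities that require active management will be recorded as AEs or SAEs on the CRF". The examples include dose modification and discontinuation, and extend to "more frequent follow-up assessments, further diagnostic investigation, etc".
- **Routine reporting (10.1.3).** Table 8, for phase 1 studies, calls for every grade from 1 to 4 at every attribution. Table 9, for phase 2 studies, calls for Grades 3 and 4 at every attribution, and Grades 1 and 2 when at least possibly related. Neither has a management condition.
- **Analysis (12.4.1).** "The frequency of toxicities will be tabulated by maximum grade by preferred term within a patient across all cycles". Section 12 plans no table of laboratory values, laboratory grades or shifts.
- **Tests (8.2 to 8.7, Table 4).** Hematology and the metabolic panel with magnesium are scheduled at baseline and on Day 1 of every cycle, a basic panel with magnesium on Days 8 and 15, and thyroid tests at baseline and every second cycle from Cycle 2.
- **Magnesium (6.4.2).** "Magnesium levels are to be monitored and levels replaced on therapy and up to 8 weeks after completion of therapy, as per practice standard".

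**The concern.** A laboratory abnormality must pass two judgements before it reaches the CRF: that it is clinically significant, and that it requires active management. The list of qualifying actions is open-ended. The definition and the two reporting tables set neither condition. Two sites could each follow a defensible reading of the protocol and record the same value differently.

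At stake is the laboratory part of a primary objective. Sections 1.2 and 1.5 list hypomagnesemia among the common effects of anti-EGFR therapy, and 1.5 reports Grade 3 or higher transaminase rises when EGFR inhibitors were combined with PD-1 or PD-L1 antibodies. Patients with liver metastases may enter with AST and ALT up to 5 times the upper limit of normal (5.1), so change from baseline matters as well as the level reached. The planned table shows no such change.

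**Working it through.** The plan gives no figure for laboratory toxicity, so there is none to reproduce. The check is mainly one of reading.

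**Step 1. Which rule governs?** If 10.1.1 and Tables 8 and 9 govern, an abnormal finding is an adverse event and is reported by grade and attribution. If 10.1.1.3 governs, only those passing both judgements are recorded. It is the more specific text and names the CRF, so a site may well follow it. The protocol does not say which prevails. I take the 12.4.1 table to be built from recorded events, because it works by preferred term.

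**Step 2. Where does the protocol fix the trigger?**

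| Test | Trigger set by grade or value | Left to judgement under 10.1.1.3 |
|---|---|---|
| AST, ALT | Table 1 (Grade 2 and above, drug-related); closer testing at Grade 2 (6.3.7); Table 10 at Grade 2 and above; liver injury criteria (10.3) | Mainly Grade 1 |
| Creatinine | Table 10 at Grade 3 and above, or any grade leading to dose modification or systemic steroids | Lower grades without these |
| Anemia | Table 10 at Grade 4, whatever the mechanism | Below Grade 4, unless Table 1's catch-all row applies |
| Neutrophils, lymphocytes, platelets | Table 10 only for named syndromes; Table 1 catch-all for drug-related Grade 3 and 4 | Counts not attributed to drug, and lower grades |
| Thyroid | Table 10 at Grade 3 and above, or Grade 2 and above leading to dose modification or systemic steroids; Table 1 for hyperthyroidism | Asymptomatic lower-grade change |
| Magnesium | No row in Table 2, no entry in Table 10; the dose-limiting toxicity definition (12.5) addresses only Grade 4 that persists | Most of the range; replacement follows local practice |

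Section 10.4.1 makes events of clinical interest reportable regardless of attribution, so the Table 10 triggers do not depend on a causality call.

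**Step 3. What could the filter do?** The documents give neither input, so both are assumed. Let *p* be the true proportion of patients with a graded change in one test, and *m* the share of those judged to require active management. Then expected recorded patients = 42 × *p* × *m*.

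| *p* | *m* = 1 | *m* = 0.75 | *m* = 0.50 | *m* = 0.25 |
|---|---|---|---|---|
| 0.10 | 4.20 | 3.15 | 2.10 | 1.05 |
| 0.30 | 12.60 | 9.45 | 6.30 | 3.15 |
| 0.50 | 21.00 | 15.75 | 10.50 | 5.25 |

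Take *p* = 0.30. With full recording, about 13/42 would appear (exact 95% interval 17.6% to 47.1%). With *m* = 0.50, about 6/42 = 14.3% would appear (5.4% to 28.5%), an interval that excludes the true 30%.

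For sites, assume an equal split of 42/3 = 14 patients and the same true rate of 30%, or 14 × 0.30 = 4.2 patients each. A site recording 90% of changes would show 14 × 0.30 × 0.90 = 3.78, and one recording 30% would show 14 × 0.30 × 0.30 = 1.26.

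These figures show the mechanism. They do not estimate its size in this trial.

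**The case against.** The best defence is that the rule is a deliberate and broad filter. It speaks of abnormalities that *require* management, and a repeat test or a diagnostic work-up qualifies. A reader might infer that a laboratory toxicity counts only when someone treats it, so that the laboratory results would simply reflect local treatment habits. The text does not support that. For transaminases, the laboratory signal that the background reports for such combinations, the protocol sets grade-based triggers.

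A reader might also infer that high-grade values not attributed to study drug routinely go unrecorded. Table 9 calls for Grade 3 and 4 events even when unrelated, so this follows only if 10.1.1.3 overrides Table 9. The text leaves that open, which is a reason to reconcile the sections but not proof of loss.

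On magnesium, 6.4.2 does call for monitoring and replacement, and replaced hypomagnesemia meets the recording rule. What varies is the level at which a site replaces.

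Finally, the objective is descriptive and no decision rule depends on it. All of this stands, and it narrows the point. It does not answer the remainder: for the tests in the last column of the Step 2 table, entry into the only planned safety table can turn on judgement, and no planned analysis shows what was missed.

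**Conclusion.** The concern holds in a limited form. The laboratory part of a primary objective depends partly on investigator judgement, under a recording rule narrower than the protocol's own definition and reporting tables. The exposure is chiefly hypomagnesemia, cytopenias outside Table 10, and low-grade asymptomatic changes. Recorded rates for these can be too low and can differ between sites.

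The size cannot be known from the documents, and any count of missing patients would rest on assumed rates such as those above. The conclusion also rests on reading 12.4.1 as a table of recorded events. It should not be taken to mean that graded laboratory values already exist: the documents schedule the tests but apply CTCAE grading to adverse events. Sample size, power, type I error and the dose-limiting toxicity rule are unaffected. This is a cheap improvement, not a flaw that threatens the trial.

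**What to change.** 1. Keep the CRF rule in 10.1.1.3, but state how it relates to 10.1.1 and Tables 8 and 9, so that all sites apply one rule to laboratory findings.
2. Add to 12.4.1, beside the adverse event table, along these lines: *For each scheduled hematology, chemistry, magnesium and thyroid test, the worst on-treatment CTCAE v4.0 grade, derived from the scheduled values, will be tabulated for all treated patients, with shift from baseline grade. Where a test has no value-based grade, shift against the site reference range will be shown.*

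The shift matters because some patients enter with abnormal values. The table will still reflect any magnesium replacement given between samples, so it complements the adverse event table and does not replace it.

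The cost is some programming, plus data entry if scheduled values and site reference ranges are not already in the study database. Section 15.1 does not say whether they are. No visit, test or clinical management rule changes.
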